Design. A group of 6 hemianopic participants will be pre-screened for suitability and baseline (pre-training) performance will be acquired on the battery of visual tasks (see below) and be administered the low-vision visual functioning questionnaire (LV-VFQ-48) to assess quality of life, a dilated ophthalmic exam including Optical Coherence Tomography of the macula/RNFL, a kinetic visual field test with size V, and a 30-2 humphrey visual field with Size V. If the participant has a recent 30-2 exam on file, this may be used instead of collecting a new exam. Participants will receive a second kinetic visual field test and a 30-2 visual field test at the end of the study to measure any changes according to the clinical standard.

They will participate in weekly sessions (1.5-2 hrs) for the next three months. This purposely extends well beyond the window of expected recovery. In initial (“training”) sessions, subjects will be exposed (and respond) to spatiotemporally congruent pairs of visual-auditory stimuli presented within their blinded field, with occasional probes of unisensory visual stimuli on both sides of space. Once recovery of visual responsiveness in the contralesional field is observed, sessions will alternate between “training/testing” and “testing only” sessions in which performance on the visual battery will be re-assessed. Because this is a pilot study, the testing battery is extensive. However, the principal hypotheses and predictions are qualitative: subjects will either be able to perform a visual task at some level or not at all.

A high-speed digital video camera mounted behind the participant will record overt movements for later analysis using manual or automated scoring. The subject’s face is not included on the video, however, the video obtained contains potentially identifying information and will be secured on an encrypted drive. Multiple data points will be extracted: latency of the initiation of the motor movement, during of execution, and final position. These multiple measures will then be analyzed alongside other data points for the subject after anonymization to determine their changes during the course of experimentation and prognostic value in treatment outcomes.

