apparatus calibration. Each trial begins after subjects fixate for 500 ms on a central fixation spot. After a brief (300-600 ms) delay, either a training stimulus (3 f.c. bright light from LED + 75 dB broadband sound from speaker) is activated at 45° of eccentricity in the blind field, or (with lower frequency) a single visual stimulus with same parameters is activated at 45° in the intact or blinded field, or no stimulus is presented at all. Subjects are requested to saccade to any stimuli that appear and otherwise maintain fixation. Stimuli remain active for 3 seconds or for 500 ms after a saccade is made, whichever is shorter. Multisensory training the VR apparatus uses an identical procedure, with the visual and auditory stimuli being an equivalent stimuli produced at the same virtual distance and positions. Trials are presented at a rate of 1/5 sec and continue for 60 mins. Depending on whether it is a purely training or training/testing session, this allows for 500 – 1000 presentations of the visual-auditory training stimulus per session along with 200-400 trials containing single visual or no stimuli. This greatly exceeds the number required in the animal model, and provides the best opportunity for success in sessions of practical duration.

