Subjects selection criteria. To maximize the potential for success, adults aged 18-85 of either sex will be selected based on: (1) diagnosis of a stable homonymous hemianopia (>4 weeks) with absence of hemineglect, (2) a lesion encompassing at least primary visual cortex but sparing parietal cortex, (3) normal auditory and cognitive function, (4) willingness to participate in the three month program, (5) ability to perform the visual discriminations in their intact field. Multiple (n=6) subjects will be recruited for left- and right-sided lesions. Because this is a pilot program, variance across other demographics (e.g., age, gender, race, stroke type) will be noted but are unlikely to be able to be statistically evaluated.

Interventions and Interactions. Subjects will participate in weekly sessions (1.5-2 hrs) for three months, which contains baseline testing, training, repeated testing of visual recovery, and patients will be asked to keep a diary of their experiences with the training, describing what/when they can see. No formal diary will be given to the subject, but asked to write down experiences in a notebook as needed. These pages will be collected at the corresponding study visit and labeled with the subject visit and study identification number by the study coordinator. Training and testing are performed while subjects are comfortably seated and viewing either an array of LEDs and speakers (perimetry apparatus), or VR-integrated screen. Their eye position is tracked. Each trial is participant-initiated by an input device (key press or trigger). After a brief period either no stimulus is presented (“catch trial”), or a selected visual, auditory, or visual-auditory stimulus (or multiple stimuli) will be presented, and the participant makes a response decision, indicating the location of a stimulus in the field, or indicating its identity or identity relative to a co-presented stimulus, and/or indicating confidence in judgment. Responses are indicated either by eye movement, pointing gesture, pointing device, or verbal report (transcribed by experimenter). All stimulus presentations are under the participant’s control, and they may freely pause or abort the experiment at any time by verbal statement or failure to fixate. Repeat testing will be attempted if the participant aborts testing after a period of rest.

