Outcome Measure(s). A variety of dependent measures are extracted during these experiments, including responses selected, response delay/timing, response accuracy, etc. Responses to visual stimuli will be evaluated over the duration of the experiment to assess recovery of function. The main hypotheses state that subjects will either be able to perform some task at some level or not at all, although there is likely to be quantitative variation in parameters such as response latency, threshold sensitivity, and confidence. In this context, recovery of any visual function is a success. Below we outline two sets of predictions identifying the most credible outcomes and elaborate on the significance of each, although mixed results are also possible.

Modest Rehabilitation: It is possible that hemianopic patients will recover basic reflexive visual functionality, but their capabilities will be limited to those typically associated with “blindsight”. In this case, they would be able to detect and localize visual stimuli in the rehabilitated field and use auditory information to enhance this capability. However, they would always choose the intact field in competition tasks, be unable to perform any higher-order discriminations in the contralesional field, and would always

have low confidence in that field even when they can perform visually – a result falling short of that seen in the animal model. Such a result will be less than expected but is not without clinical value: by acquiring the ability to respond to contralesional visual stimuli, rehabilitated subjects can bring them into the sighted field for further analysis.

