The Expected Result: However, our expectation is that hemianopic patients will recover visual functionality similar to that observed in the animal model, although the timing of the recovery and the quantitative parameters of the functional endpoints may differ. This means that, after a few weeks of training, they will be able to perform each of the tasks at some level under some conditions. We expect performance to be best under scotopic conditions and for moving stimuli; i.e., testing conditions best suited to driving robust visual responses in SC-mediated visual pathways. There is likely to be an initial separation between performance in visual tasks and confidence, with the former recovering faster than the latter, as the brain adapts and reinterprets activity patterns in remaining circuits as definitive of the visual stimuli generating them.

In either case, future directions will examine the means to improve the rehabilitation method (including calibrating subjects to the sensation of contralesional visual stimuli), examining the impact of the strategy on other domains impacting quality of life (e.g., navigation), an analysis of the underlying circuits using magnetoencephalography, evaluation of the sensitivity of different individual features to the procedure (e.g., age, gender, delay from lesion onset to treatment), a deeper exploration of the limits of functional recovery, and the formalization of a clinical trials protocol.

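### Neither the entry criteria nor the success rule requires absent blind-field vision at baseline, so residual vision, or practice gains in it, could be read as recovery

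*Combined protocol and SAP*

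**What the plan says.** **Entry.** Subjects selection criteria, repeated under Subject Recruitment Methods, asks for "1) diagnosis of a stable homonymous hemianopia (>4 weeks) with absence of hemineglect", a lesion covering at least primary visual cortex, normal hearing and cognition, willingness to take part, and "5) ability to perform the visual discriminations in their intact field". The last is the only criterion tied to the study's tasks, and it concerns the seeing side.

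**Baseline.** Design states: "A group of 6 hemianopic participants will be pre-screened for suitability and baseline (pre-training) performance will be acquired on the battery of visual tasks". A kinetic field and a 30-2 field, both with size V, are also taken before training and at the end.

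**Training.** The training stimulus "is activated at 45° of eccentricity in the blind field". Visual-only probes at 45° are described only as part of training trials. In Visual tests, the Detection/Localization target appears at a random position outside central space.

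**Success.** Design and Outcome Measure(s) both frame the main hypotheses as all-or-none: a participant can do a task to some degree, or cannot do it. Outcome Measure(s) adds: "In this context, recovery of any visual function is a success". Its lesser outcome, Modest Rehabilitation, is limited to blindsight-type function, in which "they would be able to detect and localize visual stimuli in the rehabilitated field" but with low confidence. The Expected Result says: "We expect performance to be best under scotopic conditions and for moving stimuli".

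**Switch.** Design: "Once recovery of visual responsiveness in the contralesional field is observed, sessions will alternate between" training/testing and testing-only sessions.

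**Analysis.** The Analytical Plan compares the clinical tests before and after training. It models battery thresholds, maximum accuracy, confidence and latency for change over time.

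**The concern.** With one group and no control, an all-or-none outcome shows recovery only if the function was absent at entry. The protocol's lesser outcome is an ability that some patients with this diagnosis might already have: detecting and localizing with low confidence, perhaps only in the dark or for moving targets. A partial defect that spares the tested location raises the same problem. Nothing in the five criteria excludes either patient. Neither the success statement nor the switch says that a task must have been failed before training, or how good later performance must be. At stake is whether the proof-of-concept claim means restored function or better use of function that was never lost.

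**Working it through.** The documents give no alpha, response threshold or justification for six participants on this point, so there is no planned figure to reproduce. The check has three parts.

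**1. Where baseline enters**

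| Element | Baseline measured? | Role of baseline stated? | Threshold stated? |
|---|---|---|---|
| Entry criteria 1–5 | Not for the blind field | No | No |
| Clinical fields before/after | Yes | Yes, as change | No |
| Model of the battery over time | Yes | Yes, as change | No |
| All-or-none success statement | Yes, but not referred to | No | No |
| Switch to alternating sessions | 45° visual probes described only within training | No | No |

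**2. How much a baseline rule matters**

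Document input: a run is 10–12 trials. Two runs at 1–4 stimulus levels form a block, and 2 × 10 × 1 = 20 to 2 × 12 × 4 = 96 agrees with the stated block size. One stimulus level therefore gets 20–24 trials per block. These are shared between both sides of space and, for detection, with no-stimulus trials, so the blind-field count is smaller still.

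Assumptions, not in the documents: a constant per-trial hit probability p in the blind field, independent trials, no training effect, guessing ignored, and success read at its most lenient as any hit.

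- No baseline rule: A = 1 − (1 − p)^n
- Also requiring zero hits in a matched baseline block: B = (1 − p)^n × A

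| n | p | A | B |
|---|---|---|---|
| 10 | 0.05 | 0.401 | 0.240 |
| 12 | 0.05 | 0.460 | 0.248 |
| 20 | 0.05 | 0.642 | 0.230 |
| 20 | 0.10 | 0.878 | 0.107 |
| 20 | 0.20 | 0.988 | 0.011 |
| 20 | 0.30 | 0.999 | 0.001 |
| 24 | 0.10 | 0.920 | 0.073 |

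Among six such unchanged participants at p = 0.10 and n = 20, the expected number called recovered is 6 × 0.878 = 5.3 without the rule and 6 × 0.107 = 0.6 with it.

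Two cautions follow.

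- A short baseline is weak evidence of floor. At p = 0.10, the chance of no hits is 0.90^10 = 0.35 in 10 trials and 0.90^12 = 0.28 in 12.
- The size depends on the unstated threshold. If success needed at least 50% hits in 20 trials, an unchanged participant would pass with probability 0.003 at p = 0.20 and 0.048 at p = 0.30.

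**3. Chance that such a patient enters**

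If a share q of eligible patients has residual ability, at least one of six has it with probability 1 − (1 − q)^6:

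- q = 5%: 1 − 0.95^6 = 26%
- q = 10%: 1 − 0.90^6 = 47%
- q = 20%: 1 − 0.80^6 = 74%

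The q values are assumed. This is the chance of entry, not the chance that such a patient is miscounted as recovered.

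**The case against.** The strongest reply is that the plan measures baseline and analyses change. Stable residual vision would appear in the pre-training battery and fields, and would contribute no gain in the Analytical Plan's comparisons. The success sentence speaks of recovery, and the Modest Rehabilitation paragraph speaks of acquiring an ability. The lesion criterion, the description of participants as blind on one side and the pre-screening for suitability all point to dense defects. The switch only changes session type and is not an endpoint. This is also a small pilot meant to inform later studies.

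Most of this stands, and it rules out several readings that a reader might infer:

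- **That pre-existing vision will be counted as recovery and reported as proof of concept.** The documents do not support this. The rules fail to prevent it, which is a weaker statement.
- **That the 30-2 field cannot reach 45°.** The documents do not give its extent, so this would be an assumption. The point does not need it.
- **That the baseline battery already settles whether 45° is blind.** Detection targets are placed at random, so sampling at 45° is not assured.

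The reply does not close the gap. The change model is not the stated success rule, and Design calls the principal hypotheses qualitative. A change model also cannot separate practice gains in residual vision from restored function, since both are positive change. Apparatus does not require fixation to be held during stimulation, so scanning could produce hits. Testing structure allows testing to be tailored to each participant and does not exempt baseline, so some baseline cells may be thin. Neither the description as blind nor the pre-screening is tied to a test result.

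**Conclusion.** The point holds in a limited form. No criterion requires absent blind-field performance on the study's tests or at 45°, and the all-or-none success statement and the switch give neither a role for baseline nor a threshold. Blindsight-type or partial vision, or practice gains in it, could therefore be read as recovery of lost function.

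The size cannot be fixed from the documents, which give no prevalence of residual vision and no threshold. Under the most lenient reading, with assumed residual hit rates of 5% to 30% and 20 trials, 64% to 99.9% of unchanged participants would count as able to perform. A zero-hit baseline rule lowers this to between 23% and 0.1%. The 23% belongs to the lowest hit rate, so a baseline rule also needs enough trials.

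This should be fixed before results are interpreted. It does not invalidate the design, because most of the data needed are already scheduled.

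**What to change.** Define recovery in Outcome Measure(s), per participant and per test-by-condition cell (test, light level, stationary or moving), as both:

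1. blind-field performance at floor before training; and
2. later blind-field performance above chance.

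In both steps, compare hits at the highest contrast with the same participant's rate of catch-trial responses that would have fallen within the same <10° window around a nominal target position. Without that window, the comparison sets a localized hit against a response made anywhere.

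State in advance the number of baseline blind-field trials and the statistical threshold. A single run of 10–12 trials is too short to exclude low residual vision.

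Also:

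- Include visual-only blind-field trials at 45° in the existing baseline session, before any training.
- Apply the same definition to the switch. State what happens for a participant with no cell at floor; that choice is for the investigator.
- Report change in cells not at floor at baseline separately, as improvement of residual vision and not as recovery.

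Screening out on the kinetic field or on baseline performance is optional; the rule above keeps every participant.

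Cost: a short amendment and some added trials in a session that already takes place. The downside is that fewer cells can count towards success.

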Visual tests: Tests of vision will be conducted on both sides of space and are organized in trials. In each trial the subject acquires fixation for 500 ms before a stimulus is presented after a randomized delay (200-600 ms). Subjects are required to saccade or point to (i.e., “indicate”) the stimulus or stimulus-target (<10° error) within 2 seconds or their response is scored as a “No-Go”. They are informed of whether their response was “correct” or “incorrect” via an auditory tone after a confidence report (see below). Each test has one or more stimulus levels that are manipulated to create the independent variable(s) of psychometric functions of performance. Detection/Localization: Trials contain either a visual target (LED or 5X5° white square) of manipulated contrast at a randomly-selected location outside of central space (correct response: indicate), or no stimulus anywhere (correct response: No-Go). Competition: Trials contain either no stimuli (correct response: No-Go), or 1 stimulus at a randomly-selected location on either side of space (correct response: indicate), or 2 identical visual stimuli at homotopic locations with randomized eccentricity (correct response: indicate both). Stimulus contrast is manipulated. Multisensory Integration: Trials contain either no stimuli (correct response: No-Go) or brief (100 ms) low-contrast visual or low-volume auditory stimuli presented alone or together at a randomly-selected location (correct response: “indicate”). This evaluates whether the senses can be used synergistically in contralesional space to enhance localization as in intact subjects. Frequency Discrimination: Pairs of oriented gratings with manipulated Δ° and Δf presented on either side of space (correct response: indicate if same, No-Go if different). Shape Discrimination: Unilaterally-presented pairs of simple Efron shapes (see (Whitwell et al., 2014)) with manipulated similarity (correct response: indicate if same, No-Go if different). These shapes consist of stacked rectangles or smoothed splines whose similarity can be quantitatively manipulated and provide a robust, common, and controlled way of assessing shape perception in normal and compromised populations. Subjects will also have the opportunity to report qualitative aspects of any changes in their visual perception during the study.

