Testing conditions: Each of the above tests will be evaluated under two different ambient light conditions: normal indoor levels (~300 lux) and darkness (~.001 lux). Lighting conditions are set during the “briefing” period and changed during the “break” (see below), which gives time for dark- or light-accommodation. We will also evaluate conditions in which stimuli are either stationary or moving.

Confidence reports: Subject performance is tracked online and summarized in a numeric “game score” displayed to them after each testing run (see below). On each trial, after making their response (either indicating or No-Go), subjects verbally report a confidence score of 1-3 indicating their confidence in whether they are guessing (1), are unsure (2), or are very confident (3) in their response. The confidence rating translates to the points wagered for that trial. Correct responses increase the game score by double the wagered amount, while incorrect responses decrease the score by the wagered amount.

Testing structure: A 2 hr testing session is divided into two 45-min sets separated by a 10 min “break”, with a 10 min “briefing” period at the beginning and 10 min “recapitulation” period at the end.

Training/testing sessions contain only a single set. Each trial requires <3-5 seconds. Trials of a single task, stimulus level, and testing condition are conceptually organized into “runs” of 10-12 trials (~.75-1 min/run with warmup/cooldown). Two runs with the same task and testing condition, but 1-4 stimulus levels, are intermixed within a “block” of 20-96 trials (2-8 min/block). This structure provides ample time to test two blocks of each visual test (e.g., one block stationary, the other moving) within each set. However, testing will be customized for each subject in this pilot to focus on performance limits; e.g., by reducing testing of basic capabilities in later sessions, not extensively testing multiple levels of higher-order capabilities when lower-level ones are not yet intact, and initially testing with wider ranges of stimulus levels before proceeding to narrower ranges.

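### The success rule has no chance level, accuracy threshold, multiplicity control or required number of participants, so chance performance could meet it

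*Combined protocol and SAP*

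**What the plan says.** - **Success rule (Outcome Measure(s)):** "In this context, recovery of any visual function is a success". The main hypotheses there are that "subjects will either be able to perform some task at some level or not at all". Design says almost the same and adds that "the principal hypotheses and predictions are qualitative".
- **Expected finding (The Expected Result):** after a few weeks of training, "they will be able to perform each of the tasks at some level under some conditions".
- **Tests (Visual tests):** there are five: Detection/Localization, Competition, Multisensory Integration, Frequency Discrimination and Shape Discrimination. "Tests of vision will be conducted on both sides of space and are organized in trials".
- **Conditions (Testing conditions):** "Each of the above tests will be evaluated under two different ambient light conditions". Stationary and moving stimuli are compared as well.
- **Amount of testing (Testing structure):** runs have 10 to 12 trials, with 1 to 4 stimulus levels per block. Testing is tailored to each participant.
- **Participants (Design):** "A group of 6 hemianopic participants will be pre-screened for suitability". There is no control group.
- **Comparators collected:** the same battery before training (Design), no-stimulus trials and intact-side testing (Visual tests), visual fields before and after (Design, Analytical Plan), and a multilevel regression of change over time and side of space (Analytical Plan).

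No section states a guess rate, a minimum accuracy, a test against chance, an allowance for multiple looks, or how many participants must recover. It is also not said whether success is judged per participant or for the study.

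**The concern.** The rule is an OR over many test-by-condition cells, and what counts as performing at some level is undefined. Chance performance on these tasks is not zero. Two of the tests have same/different answers, and localization accepts any response within 10° of the target. A participant with no recovery can therefore look able in some cell.

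The Background presents the study as proof-of-concept evidence to support further funding and large trials. A go signal of that kind needs a rule that could also return a no, and this one has no stated way to do so. The comparators that could supply it are collected but play no part in the call.

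**Working it through.** The documents give no alpha, power or false-success rate, so there is no figure to reproduce.

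**Cells.** 5 tests × 2 light levels × 2 motion conditions = 20 per participant; × 6 participants = 120.

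**False success with no effect.** Assume that all cells are run, that they are independent, and that each has false-positive rate a. The chance of at least one false positive in k cells is 1 − (1 − a)^k.

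| Assumed a | One participant (k = 20) | At least one of six (k = 120) |
|---|---|---|
| 5% | 64.2% | 99.8% |
| 2.5% | 39.7% | 95.2% |
| 1% | 18.2% | 70.1% |
| 0.1% | 2.0% | 11.3% |

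**Correlation.** Cells within a participant are unlikely to be independent. A simulation with equally correlated normal scores (20 cells, six independent participants, 100,000 replicates) gives these chances of at least one false success among six:

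| Correlation | a = 5% | a = 1% |
|---|---|---|
| 0.3 | 97% | 59% |
| 0.5 | 92% | 48% |
| 0.8 | 72% | 28% |
| 1.0 | 26% | 6% |

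**What a could be at the plan's run lengths.** Take only the two same/different tests and assume a 50% guess rate (balanced trials). They contribute 2 × 2 × 2 = 8 cells per participant and 48 in all.
- 8 or more correct of 10: tail probability 0.055; 1 − (1 − 0.0547)^48 = 93%.
- 10 or more correct of 12: tail probability 0.019; 1 − (1 − 0.0193)^48 = 61%.

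**Requiring failure at baseline as well.** For the 8-of-10 rule, the chance of failing first and passing later is 0.9453 × 0.0547 = 0.0517. Over 48 cells this gives 1 − (1 − 0.0517)^48 = 92%, so a baseline condition of this kind barely helps.

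**What the count of 20 leaves out.** Several stimulus levels and repeated sessions add chances. Tailored testing removes some.

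**The case against.** **The study is a pilot.** It has six participants and openly qualitative hypotheses, and Analytical Plan says its estimates are meant to guide later work. Confirmatory error control would be out of proportion. This stands as to severity. It does not excuse a success rule with no threshold.

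**Comparators exist, and recovery implies change from baseline.** This is true, and the data are a real strength. But nothing links them to the success call.

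**A participant with no effect may never see all 20 cells.** Design begins re-testing the battery only once some contralesional responsiveness is seen, and Testing structure limits higher-order testing while basic abilities are absent. This stands against the larger figures. It does not remove the concern, because the trigger for re-testing is itself undefined.

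**Stronger readings that the documents do not support.**
- A reader might infer that a success call is nearly certain, or that the study cannot fail. That needs success judged as any cell in any participant, a rate of about 2.5% to 5% per cell, no strong correlation and a full battery. The plan fixes none of these.
- A reader might take blind guessing to be right 20/90 = 22% of the time. That assumes a response on every trial, always to the correct side. Guesses spread over 180° give 20/180 = 11%, and withholding a response lowers it further.
- A reader might argue that training builds a habitual saccade to 45° that then passes for recovery. The Detection/Localization test uses randomly chosen locations, so the habit does not carry over as such. In training it would also produce errors on no-stimulus and intact-field trials. The share of training trials at that spot is not fixed either: the stated ranges allow 500/900 = 56% to 1000/1200 = 83%.

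**Conclusion.** The concern holds in this form: the plan states a permissive success rule without a chance level, accuracy threshold, multiplicity control or participant count, and does not connect its own comparators to that rule. Following it as written can produce a proof-of-concept claim by chance.

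The documents do not determine how likely that is. If all 20 cells are run and independent, the chance of at least one false success among six runs from 11% (0.1% per cell) through 70% (1%) to 99.8% (5%). Per participant it runs from 2% to 64%. Correlation or untested cells lower these figures; extra stimulus levels and sessions raise them. Because no criterion is set, nothing holds the rate at the low end. For a pilot this should be fixed, but it does not invalidate the design.

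**What to change.** **Deciding outcome.** Name blind-field Detection/Localization in one pre-specified condition, with stimulus type and contrast fixed. Darkness with moving stimuli is a natural choice, since The Expected Result predicts the best performance there. Run a fixed block of about 40 blind-side target trials and 40 no-stimulus trials at baseline and at the final visit. State that this block is exempt from the planned reduction of basic testing in later sessions.

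**Participant rule.** Count a participant as recovered only if final correct-location responses exceed both:
1. that participant's own baseline hits (one-sided exact test of change at 1%), and
2. responses to the same region on the final no-stimulus trials (one-sided exact test at 1%).

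**Study rule.** Claim proof of concept if at least 2 of 6 recover. Report every other test and condition descriptively, with its chance level.

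**Why change must be tested directly.** Passing at the end but not at baseline is not a test of change. With an unchanged 25% hit rate and 5% false alarms, a participant passes the no-stimulus comparison with probability 0.485 at each visit. Such a participant would be called recovered with probability 0.485 × 0.515 = 0.25, and two or more of six would be with probability 1 − 0.75^6 − 6 × 0.25 × 0.75^5 = 0.47.

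**Performance of the proposed rule.** With no change from baseline, including stable blindsight-type ability, each participant is falsely counted with probability at most 1%. The study claim is then false with probability at most 1 − 0.99^6 − 6 × 0.01 × 0.99^5 = 0.0015. With 5% baseline hits and 5% false alarms (both assumed) and independent trials, power per participant is about 0.57, 0.90 and 0.99 at final hit rates of 30%, 40% and 50%. If all six reach only 30%, the study claim is met with probability 1 − 0.43^6 − 6 × 0.57 × 0.43^5 = 0.94.

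**Cost.** Edits are needed to Outcome Measure(s), Analytical Plan and Testing structure. The 80 trials at up to 5 seconds take 400 seconds, about 7 minutes, at each of two visits; interleaving 40 intact-side targets would make it 120 × 5 = 600 seconds, or 10 minutes. The success claim becomes stricter. The rule guards against chance; without a control group it does not show that training caused the change.
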